7.3 Exploratory Analyses Not Planned in Accordance with the Protocol

Not applicable.

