11.5 Final Analysis Plan

The final analysis will be used to evaluate the safety, tolerability, and immunogenicity of two IM doses of ID93 + GLA-SE in the single-vial or two-vial presentations at study Days 0 and 56.

A detailed Statistical Analysis Plan will be developed prior to study completion and database lock. The analysis will consist of baseline and demographic data, safety data, immunogenicity data, and laboratory data. Data will be summarized with standard descriptive statistics and provided in tables, listings, and figures as appropriate.

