1 INTRODUCTION

Note: The safety analysis has already been performed. This amendment is to the immunology section only.

The purpose and scope of this document is to describe the statistical analysis plan (SAP) that will guide the analysis of the clinical safety, IgG ELISA, ELISpot, and ICS data (primary and secondary study objectives and endpoints) for the final study report for protocol IDRI-TBVPX-120.

The clinical study report will be prepared after all study subjects have completed all study visits, all data in the clinical study database have been reviewed, all data queries have been resolved, the clinical database has been locked, and all immunology laboratory assays have been completed. All individual subject data listings, summary tables, and statistical analyses described below will be provided in separate appendices to the study report. Unless otherwise indicated, all listings and summary tables will be provided by treatment group.

This SAP is written with consideration of the recommendations outlined in the International Conference on Harmonization (ICH) E9 Guideline entitled Guidance for Industry: Statistical Principles for Clinical Trials¹ and the ICH E3 Guideline entitled Guidance for Industry: Structure and Content of Clinical Study Reports².

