2.3 Exploratory Objective

- To further evaluate the immunogenicity of ID93 + GLA-SE following two IM injections administered on Days 0 and 56 by measuring mycobacterial growth inhibition, quantifying IgA levels in mucosal secretions, and measuring frequencies of circulating T follicular helper cells, antibody secreting cells, and memory B cells at specified time points.

Note that the scope of this SAP does not include the exploratory objectives.

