7.2.2.3 Reactogenicity Adverse Events

Local injection site reaction adverse events (pain, induration, and erythema) and solicited systemic reaction adverse events (headache, arthralgia, chills, loss of appetite, fever, fatigue, and myalgia) will be recorded at 60 minutes and seven days after each study injection (Days 0, 7, 56, and 63). The seven day period following each study injection is referred to as the 'post-injection period'. Study injection reactions will be classified as occurring during the corresponding 7-day post-injection period (Post Injection Period Day 0-7, and 56-63) if the onset date is on or after the date and time of injection and before the seventh day after injection.

Summaries of the number (%) of subjects in each treatment group with at least one reactogenicity adverse event reported in the CRF will be provided for:

- at least one local injection site reaction
- at least one systemic reaction
- each individual event

The distribution of the maximum severity grade for the 7-day post-injection period will be summarized for each adverse event. If a subject experienced an adverse event more than once, the event with the maximum severity grade will be included in this summary.

Primary analysis of reactogenicity adverse events will be conducted in an Intent to Treat manner, that is, subjects will be classified based on the treatment group to which they were assigned. If any subjects incorrectly received an injection of product they were not assigned to receive, secondary analysis will be conducted with subjects classified based on product actually received during the study. Any subject randomized (ITT) but not enrolled (did not receive a study injection) will not be included in any analyses.

Fisher's exact tests will be used to compare the treatment groups with respect to the proportion of subjects with at least one reactogenicity adverse event. Fisher's exact tests will also be used to compare the treatment groups with respect to local site of injection reactions and solicited systemic reactions separately.

Reactogenicity adverse events will be summarized by treatment group for each 7-day post-injection period. The treatment groups will be compared with respect to the number (%) of subjects with at least one reactogenicity adverse event during each 7-day post-injection period using Fisher's exact tests.

The following proportions of adverse events will be compared across treatment groups:

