7.2.3 Immune Response

The following are the endpoints of interest:

Primary Analysis Endpoints:

- IgG antibody responses to ID93 by ELISA at Days 0, 14, 56, 70, 84, and 224
 - Mean endpoint titer of ID93-specific antibodies for total IgG on for each treatment group.
 - The proportion of subjects with at least a 4-fold increase in ID93-specific IgG antibody levels on Days 14, 56, 70, 84, and 224 relative to baseline (Day 0).
 - Mean fold change from baseline (Day 0) in IgG antibody responses to ID93.
- T cell responses to ID93 by PBMC ICS on Days 0, 7, 14, 56, 63, 70, 84, and 224
 - The proportion of cells expressing any two of IFN- γ , TNF, IL-2, IL-4, IL-21, or CD154 in response to ID93.
 - The polyfunctionality based on expression of IFN- γ , TNF, IL-2, IL-4, IL-21, or CD154.
- T cell responses to ID93 by ELISpot on Days 0, 14, 56, 70, 84 and 224
 - The number of IFN- γ cytokine-secreting cells in PBMC samples in response to the ID93 antigen relative to baseline (Day 0) at Days 14, 56, 70, 84, and 224, as assayed by ELISpot.

Secondary and Exploratory Analysis Endpoints:

- IgG subclass antibody responses to ID93 by ELISA at Days 0, 14, 56, 70, 84, and 224

- The proportion of subjects with at least a 4-fold increase in ID93-specific IgG1, IgG2, IgG3, and IgG4 antibody levels on Days 14, 56, 70, 84, and 224 relative to baseline (Day 0).
- Mean endpoint titer of ID93-specific antibodies for IgG1, IgG2, IgG3, and IgG4 on for each treatment group.

Immune responses for each treatment group will be evaluated by calculating the response rate and magnitude of response to ID93 at all timepoints for each immunologic endpoint. Comparisons of response rates for IgG and cytokine responses between treatment groups will be made using Fisher's exact tests.

The magnitude of IgG and cytokine responses will be compared between treatment groups using a Two-sample T-test if normality assumption is met or Wilcoxon Rank-Sum Test, otherwise.

Percentages of CD4+ cells producing selected immune markers will be summarized by time point and compared between treatment groups.

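### SAP 7.3 declares nothing outside the protocol, but SAP 7.2.3 contains IgG subclass and ICS endpoints, markers and visits that the protocol does not have

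*SAP*

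**What the plan says.** SAP 7.3, headed "Exploratory Analyses Not Planned in Accordance with the Protocol", contains only a statement that it does not apply. SAP 2.3 adds: "Note that the scope of this SAP does not include the exploratory objectives".

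SAP 7.2.3 sorts the immune-response endpoints under two headings. 'Primary Analysis Endpoints' holds total IgG, IFN-γ ELISpot and ICS, with ICS defined on six markers and eight days. 'Secondary and Exploratory Analysis Endpoints' holds "IgG subclass antibody responses to ID93 by ELISA at Days 0, 14, 56, 70, 84, and 224", as four-fold response and mean titer for each of four subclasses. SAP 7.2.3.2.1 plans a narrative table with p-values between treatment groups for the median and the responder rate of the 'Any Two' CD4 and CD8 responses at each visit.

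On timing, SAP 1 states: "Note: The safety analysis has already been performed. This amendment is to the immunology section only". It also says: "Unless otherwise indicated, all listings and summary tables will be provided by treatment group". The safety plan in SAP 7.2.2.3 uses Fisher's exact tests to "compare the treatment groups with respect to the proportion of subjects with at least one reactogenicity adverse event". Protocol 11.5 had said: "A detailed Statistical Analysis Plan will be developed prior to study completion and database lock".

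**The concern.** A reader of the study report uses a section such as 7.3 to tell analyses the protocol planned from those that came later. If it says there are none, every between-arm p-value in the immunology tables is read as protocol-planned. This matters because Protocol 2.2 calls the trial a bridging study, and the second immune-response goal in SAP 7.2.1 is to determine whether the two presentations differ significantly. A stray significant difference, or a run of non-significant ones, on an endpoint the protocol never named would carry more weight than it has earned.

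The ICS endpoint is the sharper case. The subclass endpoints at least sit under a heading that marks them as secondary and exploratory. The redefined ICS endpoint carries no such mark and sits under the heading that suggests the highest rank.

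**Working it through.** The plan states no figure to reproduce here. The check sets the two documents side by side and then counts comparisons.

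**Step 1. Protocol against SAP.**

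| Item | Protocol | SAP |
|---|---|---|
| IgG | IgG to ID93, no subclasses (3.2.2, 8.2.2, 11.5.3) | Total IgG plus IgG1 to IgG4 (7.2.3, 7.2.3.1) |
| ICS markers | IFN-γ, TNF, IL-2 (3.2.2) | The same three plus IL-4, IL-21, CD154 (7.2.3, 7.2.3.2.1) |
| ICS measure | CD4 and CD8 T cells producing one or more of the three (3.2.2) | At least two of the six ('Any Two'), plus selected combinations |
| ICS days after baseline | 14, 56, 70, 84, 224 (3.2.2, 8.2.2) | 7, 14, 56, 63, 70, 84, 224 |
| Rank | Secondary (3.2.2) | 'Primary Analysis Endpoints' (7.2.3) |

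The protocol does collect PBMC on Days 7 and 63, but 3.2.3 assigns those days to the antibody-secreting-cell ELISpot and to immunophenotyping, not to ICS. SAP 7.2.3 does not list the one-or-more-of-three measure as an endpoint. Whether the selected combinations recover it cannot be told, because 7.2.3.2.1 leaves their identity to the data set.

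**Step 2. Multiplicity rule.** SAP 7.2.1 tests at a two-sided 0.05 and applies Holm-Bonferroni only to pairwise comparisons among more than two categories. With two arms, nothing is adjusted across endpoints or visits.

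**Step 3. Count of non-protocol between-arm comparisons, post-baseline.**

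- 'Any Two': 2 cell types × 7 visits × 2 measures (magnitude, responder rate) = 28.
- IgG subclasses, upper bound: 4 subclasses × 5 visits × 2 measures (four-fold response, titer) = 40.
- Total, upper bound: 28 + 40 = 68. The unnamed marker combinations are not counted.

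For comparison, the protocol's secondary outcomes give about 30: total IgG response 5, IgG fold change 5, two ELISpot analytes × 5 visits = 10, CD4 and CD8 ICS × 5 visits = 10.

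**Step 4. Expected false positives if the arms do not differ.** Expected number = number of tests × 0.05.

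- 'Any Two' only: 28 × 0.05 = 1.4.
- Subclasses only, upper bound: 40 × 0.05 = 2.0.
- Both: 68 × 0.05 = 3.4.

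Under independence, the chance of at least one is 1 − 0.95^28 = 76% for 'Any Two' alone and 1 − 0.95^68 = 97% for all 68. Repeated visits in the same subjects are correlated, which would lower these two percentages but not the expected counts. Fisher's exact test is conservative, which lowers the expected counts for response rates. That affects 20 subclass and 14 'Any Two' comparisons, 34 of the 68. The other 34 are titer or magnitude comparisons by t-test or Wilcoxon test.

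**Step 5. Timing.** The safety analysis preceded this amendment, and its planned outputs are by treatment group with tests between arms. SAP Table 1 shows 25 and 23 subjects against 24 and 24 in Protocol Table 1, which look like realised counts. It is a fair inference that treatment codes were in use for safety. No text says which immunology endpoints changed with the amendment.

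**The case against.** Five points can be made for the plan.

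- Protocol 11.5.3 speaks broadly of serum IgG responses to ID93 and of T cells producing selected cytokines, and 11.5 leaves detail to the SAP. Subclasses, IL-4 and IL-21 could be called detail within that wording. This stands in part. It does not cover CD154, which is not a cytokine, the two added ICS days, or the change from one-or-more-of-three to two-of-six.
- SAP 2.3 puts the protocol's exploratory objectives out of scope, so 7.3 may have been answered in that sense. But SAP 7.2.3 itself has a heading with exploratory endpoints, and the subclasses under it are not in the protocol.
- 'Primary' may only mean the main analyses within immunology. SAP 2.1 and 2.2 do keep safety primary and immunogenicity secondary, so the heading does not change the trial's objectives. It still hides the altered ICS endpoint among protocol outcomes.
- The 40 subclass comparisons are not a planned count. The comparison table in SAP 7.2.3.1 names total IgG, subclasses are named for a line plot with 95% intervals, and SAP 7.4 lists no separate subclass comparison table. This stands: 40 is an upper bound that rests on the general sentence in 7.2.3 about comparing IgG responses.
- Protocol 11.3 says the study tests no formal hypothesis. This also stands: the issue is how results are read, not a confirmatory error rate.

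A reader might infer more: that the added endpoints were chosen post hoc, with knowledge of results by arm. The documents do not support that. The earlier SAP is not among them, the endpoints may have been in it, and the front pages where a version date would normally stand were not available to read. Protocol 5.4.2 blinds the staff who run the immunology assays. SAP 6 keeps assay data with the sponsor until transfer to the biostatistician before analysis. Analysing safety by arm does not reveal immunology by arm.

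**Conclusion.** The declaration in SAP 7.3 is wrong as written and should be corrected. This rests on comparing the two documents and needs no assumption about motive or timing. The main instance is the ICS endpoint: redefined, extended to more markers and visits, headed as primary, and given up to 28 unadjusted between-arm p-values, with about 1.4 false positives expected if the presentations do not differ. Adding every possible subclass comparison raises this to at most about 3.4, and the conservatism of Fisher's test makes it smaller. These figures assume no true difference and that every comparison is tested at 0.05.

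The timing is a reason to document, not a finding of bias. The documents establish only that the immunology section was amended after the safety analysis. They do not show what was added then, or that immunology data had been linked to treatment codes.

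**What to change.** - In SAP 7.3, replace the present entry with a list of every endpoint, marker and visit not in the protocol: IgG1 to IgG4 response and titer; IL-4, IL-21 and CD154; ICS on Days 7 and 63; the 'Any Two' measure; and the selected marker combinations, named. Label them *not in the protocol; exploratory*. Use *post hoc* only if the record shows it.
- State that between-arm p-values for these items are descriptive.
- In SAP 7.2.3, retitle the 'Primary Analysis Endpoints' heading so that the protocol's secondary outcomes stand apart from the added ICS endpoints.
- In the study report, state when each item was added relative to access to treatment codes.

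The cost is text in the SAP and a short statement in the report, with no new data. The downside is that the added endpoints carry less weight in the report.

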7.4 List of Tables, Figures, and Listings

TABLES and FIGURES:

Table Number	Title
14.1.1	Subject Disposition, Demographic, and Baseline Data: Subject Disposition: Intent to Treat Population
14.1.2	Subject Disposition, Demographic, and Baseline Data: Subject Demographic Data: Safety Population
14.1.3	Subject Disposition, Demographic, and Baseline Data: Extent of Exposure: Study Injection Administration: Safety Population
14.2.1	Safety Data: Adverse Events: Incidence of Adverse Events: Safety Population
14.2.2	Safety Data: Adverse Events: Incidence of Adverse Events by Severity: Safety Population
14.2.3	Safety Data: Adverse Events: Incidence of Related Adverse Events: Safety Population
14.2.4	Safety Data: Adverse Events: Incidence of Adverse Events Related to Study Injection by Severity: Safety Population
14.2.5	Safety Data: Adverse Events: Incidence of Adverse Events by Study Injection Interval: Safety Population
14.2.6	Safety Data: Adverse Events: Incidence of Serious Adverse Events and Adverse Events of Special Interest: Safety Population
14.2.7	Safety Data: Adverse Events: Local Reactions: Incidence of Local Injection Site Reactions by Post-injection Period and Severity: Safety Population
14.2.8	Safety Data: Adverse Events: Systemic Reactions: Incidence of Solicited Systemic Reactions by Post-injection Period and Severity: Safety Population
14.3.1	Immunogenicity Data: IgG ELISA: IgG Antibody Response
14.3.2	Immunogenicity Data: ICS: CD4 T Cell Response and Change from Baseline
14.3.3	Immunogenicity Data: ICS: CD8 T Cell Response and Change from Baseline
14.3.4	Immunogenicity Data: ELISpot: PBMC IFN- γ Response
14.3.5	Immunogenicity Data: ELISpot: PBMC IL-10 Response
Figure Number	Title
14.4.1	Immunogenicity Data: IgG ELISA: IgG Antibody Response
14.4.2	Immunogenicity Data: ICS: CD4 T Cell Subject Response by Study Day
14.4.3	Immunogenicity Data: ICS: CD8 T Cell Subject Response by Study Day
14.4.4	Immunogenicity Data: ICS: CD4 T Cell Polyfunctional Profile Plot
14.4.5	Immunogenicity Data: ICS: CD8 T Cell Polyfunctional Profile Plot
14.4.6	Immunogenicity Data: ELISpot: PBMC IFN- γ Response
14.4.7	Immunogenicity Data: ELISpot: PBMC IL-10 Response

LISTINGS:

Listing Number	Title
16.1	Subject Disposition, Demographic, and Baseline Data: Subject Disposition: Subjects Enrolled and Eligibility
16.2	Subject Disposition, Demographic, and Baseline Data: Subject Disposition: Study Summary
16.3	Subject Disposition, Demographic, and Baseline Data: Subject Disposition: Visit Summary
16.4	Subject Disposition, Demographic, and Baseline Data: Subject Disposition: Subjects Who Withdrew from the Study or Were Lost to Follow up
16.5	Subject Disposition, Demographic, and Baseline Data: Subject Demographic Data: Intent to Treat Population
16.6	Subject Disposition, Demographic, and Baseline Data: Subject Disposition: Extent of Exposure: Study Injection Administration
16.7	Safety Data: Adverse Events: Description
16.8	Safety Data: Adverse Events: Intervention
16.9	Safety Data: Adverse Events: Grade 3
16.10	Safety Data: Adverse Events: Deaths, SAE, and PIMMC
16.11	Safety Data: Adverse Events: AE Listings For Subjects Meeting Any Criterion for Suspending Study Injection
16.12	Safety Data: Adverse Events: Local Injection Site Reactions
16.13	Safety Data: Adverse Events: Solicited Systemic Reactions
16.14	Safety Data: Laboratory Studies: Hematology
16.15	Safety Data: Laboratory Studies: Serum Chemistry
16.16	Safety Data: Serum β hCG and Urine Pregnancy Test
16.17	Safety Data: Vital Signs
16.18	Clinical Data: Physical Examinations
16.19	Clinical Data: Medical History
16.20	Clinical Data: Concomitant Medications
16.21	List of Protocol Deviations
16.22	Immunogenicity Data: IgG ELISA: IgG Antibody Response
16.23	Immunogenicity Data: ICS: CD4/CD8 T Cell Response
16.24	Immunogenicity Data: ELISpot: PBMC IFN- γ and IL-10 Response

NARRATIVE TABLES

Table Number	Title
Table 4:	Summary of Demographic Data and Other Baseline Characteristics (Safety Population)
Table 5:	Summary of Study Injection Exposure (Safety Population)
Table 6:	Subjects with Adverse Events by Study Period, Injection Interval, Severity, and Relatedness to Study Injection (Safety Population)
Table 7:	Subjects with Adverse Events Occurring in ≥ 2 Subjects (Safety Population)
Table 8:	Subjects with Local Injection Site Reaction Adverse Events by Post-injection Period (Safety Population)
Table 9:	Subjects with Solicited Systemic Reaction Adverse Events by Post-injection Period (Safety Population)
Table 10:	IgG ELISA: Antibody Response to ID93
Table 11:	PBMC ICS: CD4 T Cell Response to ID93
Table 11:	PBMC ICS: CD8 T Cell Response to ID93
Table 12:	PBMC ELISpot: IFN- γ Response to ID93
Table 13:	PBMC ELISpot: IL-10 Response to ID93
